3.2 Number of Sites

Approximately 40 sites in Japan will be selected to participate in this study. Additional centers may be added.

Sites that do not enroll subjects within 3 months of site initiation may be closed.

3.3 Number of Subjects

Participants in this clinical investigation shall be referred to as “subjects”.

The number of subjects will fulfill the planned sample size of 60 subjects.

3.4 Replacement of Subjects

Subjects who are withdrawn or removed from treatment or the study will not be replaced.

3.5 Estimated Study Duration

3.5.1 Study Duration for Subjects

Subject participation is anticipated to continue for 12 months (excluding screening period). There will be a 3 month double blind, randomized period with a 9-month open label extension.

3.5.2 End of Study

Primary Completion: defined as the time when all the randomized subjects in the study have either completed the scheduled visits up to and including Week **24** or have early terminated from the study;

End of Trial: defined as the time when all enrolled subjects have either completed the scheduled visits or have early terminated from the study.

4. SUBJECT ELIGIBILITY

Investigators will be expected to maintain a screening log of all potential study candidates that includes limited information about the potential candidate (eg, date of screening). Before any study-specific procedure, the appropriate written informed consent must be obtained. **Screening is initiated from the time of obtaining informed consent. The screening period must be completed within 28 days.**

For a full list of eligibility criteria, please refer to [Section 4.1](#).

4.1 Inclusion and Exclusion Criteria

4.1.1 Inclusion Criteria

- 101 Subject who has provided informed consent/assent prior to initiation of any study-specific activities/procedures
- 102 Male or female ≥ 20 to ≤ 80 years of age, **Japanese by self-identification**, at signing of informed consent
- 103 Subject who is not at LDL-C goal as evidenced by the 2012 JAS management category and the following LDL-C levels by central laboratory at screening:
- a) Fasting LDL-C ≥ 100 mg/dL (2.59 mmol/L) for subjects with diagnosed CHD or are CHD risk equivalent or
 - b) Fasting LDL-C ≥ 120 mg/dL (3.37 mmol/L) for subjects without diagnosed CHD or risk equivalent and Management Category III
 - c) Fasting LDL-C ≥ 140 mg/dL (4.14 mmol/L) for subjects without diagnosed CHD or risk equivalent and Management Category II
 - d) Fasting LDL-C ≥ 160 mg/dL (4.9 mmol/L) for subjects without diagnosed CHD or risk equivalent and Management Category I
- 104 Subject must have tried and failed at least 2 statins with failure to at least 1 of the statins at an average daily dose at or below the following doses due to intolerable myopathy, ie, myalgia (muscle pain, ache, or weakness without CK elevation), myositis (muscle symptoms with increased CK levels), or rhabdomyolysis (muscle symptoms with marked CK elevation). For subjects that developed rhabdomyolysis, defined as CK $> 10 \times$ ULN, failure of only 1 statin at any dose is acceptable. **Symptoms must have resolved or improved when statin was discontinued or the dose was reduced.**

- Atorvastatin 10 mg
- Fluvastatin 20 mg
- Pravastatin 10 mg
- Rosuvastatin 2.5 mg
- Simvastatin 5 mg
- Pitavastatin 1 mg
- For unlisted statins, the average daily dose should not exceed the lowest available **recommended** starting dose approved by the **Japanese Ministry of Health, Labour and Welfare**.

105 **Subjects taking bile-acid sequestering resins and/or stanol, stanol esters, low (lowest available recommended starting dose approved by the Japanese Ministry of Health, Labour and Welfare) or atypical dose of statin must be on a stable dose for at least 4 weeks prior to screening. No adjustments to statin (or other lipid lowering therapy) dose are allowed during screening and throughout study.**

EXCEPTION: if subject is on ezetimibe at start of screening it must be discontinued for ≥ 1 week before LDL-C screening

106 Fasting triglycerides ≤ 400 mg/dL (4.5 mmol/L) by central laboratory at screening

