5. SUBJECT ENROLLMENT

Before subjects begin participation in any study-specific activities/procedures, Amgen requires a copy of the site's written institutional review board/independent ethics committee (IRB/IEC) approval of the protocol, informed consent form, and all other subject information and/or recruitment material, if applicable (see [Section 11.2](#)). All subjects must personally sign and date the informed consent form before commencement of study-specific activities/procedures. **Screening is initiated from the time of obtaining informed consent. The screening period must be completed within 28 days.**

A subject is considered enrolled upon randomization. The investigator is to document and date this decision in the subject's medical record and on the enrollment **electronic case report form (eCRF)**.

Each subject who enters into the screening period for the study upon signing informed consent receives a unique subject identification number before any study-related activities/procedures are performed. The subject identification number will be assigned through an interactive voice/web response system (IVRS/IWRS). This number will be used to identify the subject throughout the clinical study and must be used on all study documentation related to that subject. Subjects who do not meet LDL-C eligibility criteria cannot be rescreened.

The subject identification number must remain constant throughout the entire clinical study; it must not be changed after initial assignment, including if a subject is rescreened. This number will not necessarily be the same as the randomization number assigned for the study. PPD [REDACTED]

[REDACTED]

[REDACTED]

[REDACTED]

[REDACTED]

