5.1 Randomization/Treatment Assignment

Subjects will be randomized 2:2:1:1 assignment to 4 treatment groups and will be based on a computer-generated randomization schedule prepared by Amgen before the start of the study. Randomization will be stratified by screening LDL-C concentration (< 180 mg/dL [4.66 mmol/L] vs. ≥ 180 mg/dL) and baseline **statin use**.

The following are treatment groups (2:2:1:1 respectively):

- Evolocumab SC, 420mg QM (3 AI/Pen or one Personal Injector) and PO placebo 10mg QD
- Evolocumab SC, 140mg Q2W (1 AI/Pen) and PO placebo 10mg QD
- Placebo SC 420mg QM (3 AI/Pen or one Personal Injector) and PO ezetimibe 10mg QD
- Placebo SC 140mg Q2W (1 AI/Pen) and PO ezetimibe 10mg QD

Once eligibility into the study has been confirmed, a site representative will make the randomization call to the IVRS/IWRS to assign a randomization number to the subject. The randomization call to the IVRS/IWRS is accomplished by entering the pertinent information detailed in the IVRS/IWRS user manual. A confirmation **email** will be sent to the site to verify that the correct information has been entered and to confirm the assignment of a randomization number. A subject will be considered randomized when a corresponding randomization number is assigned.

Please refer to [Section 5.2](#) below for details on when and how the randomization code may be broken. The treatment assignment date is to be documented in the subject's medical record and on the enrollment eCRF.

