7.2.5.3 Lipid Measurements

Only the screening LDL-C concentration will be reported to the site for the eligibility decision. For subjects who are rescreened, data from the first screening period will not be used for the analysis. Central laboratory results of the lipid panel, as well as ApoA1, ApoB, lipoprotein(a), and high sensitivity C-reactive protein (hsCRP) will be blinded

posttreatment to week 24 until unblinding of the clinical database. Investigators will be provided lipid results starting at week 24 until the end of study for each subject. If a lipid panel is drawn, all reasonable steps must be undertaken to avoid informing the subject and study personnel of the results.

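### Inclusion criterion 103 b, c and d: the mmol/L values (3.37, 4.14, 4.9) do not convert the mg/dL thresholds beside them (120, 140, 160); they equal about 130, 160 and 189 mg/dL

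*Protocol*

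**What the plan says.** Criterion 103 in Protocol 4.1.1 opens with "Subject who is not at LDL-C goal as evidenced by the 2012 JAS management category" and then sets four LDL-C floors, each in mg/dL with mmol/L in parentheses:

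- a) CHD or risk equivalent: "Fasting LDL-C ≥ 100 mg/dL (2.59 mmol/L")
- b) Management Category III: "Fasting LDL-C ≥ 120 mg/dL (3.37 mmol/L")
- c) Management Category II: "Fasting LDL-C ≥ 140 mg/dL (4.14 mmol/L")
- d) Management Category I: "Fasting LDL-C ≥ 160 mg/dL (4.9 mmol/L")

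Protocol 5.1 gives another LDL-C pair, the stratification cut: "< 180 mg/dL [4.66 mmol/L] vs. ≥ 180 mg/dL". Appendix D (JAS 2012) states its LDL-C targets in mg/dL only: below 160, 140 and 120 for Categories I, II and III, and below 100 with a history of CAD.

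On how the value is used, Protocol 7.2.5.3 says "Only the screening LDL-C concentration will be reported to the site for the eligibility decision", and Protocol 5 says "Subjects who do not meet LDL-C eligibility criteria cannot be rescreened". Neither section gives the reporting unit. SAP 10.3 leaves the definition of eligibility deviations to the protocol.

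**The concern.** Lines b, c and d each print two numbers that are not the same concentration. The conflict shows without any calculation. Section 5.1 equates 180 mg/dL with 4.66 mmol/L, while line d sets a larger mmol/L number (4.9) beside a smaller mg/dL number (160). Both cannot be right. Read in mmol/L, line d would also keep every Category I subject out of the lower randomization stratum, because 4.9 exceeds 4.66.

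This is an entry threshold, and a subject who fails it cannot be rescreened. A site or system working in mmol/L would turn away subjects who are above their JAS goal and meet the mg/dL rule. Amendment 1 had already cut the target from 100 to 60 subjects on feasibility grounds, so lost candidates would matter.

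The deviation record is affected too. Because the SAP takes eligibility deviations from the protocol, one subject can comply with the criterion and deviate from it at the same time.

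**Working it through.** **Conversion factor from the protocol's own pairs**

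- 103 a: 100 / 2.59 = 38.61 mg/dL per mmol/L
- 5.1: 180 / 4.66 = 38.63 mg/dL per mmol/L
- Allowing for rounding of both printed mmol/L values, the factor lies between 38.59 and 38.67.
- The response endpoint pair in 10.1.1 (70 mg/dL, 1.8 mmol/L) agrees to its one decimal: 70 / 38.61 = 1.81.

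The usual cholesterol factor, 38.67, is not given in the documents. It is used below only as the upper end of the range.

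**Ratio implied by each line of 103** (mg/dL divided by mmol/L)

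- a: 100 / 2.59 = 38.61
- b: 120 / 3.37 = 35.61
- c: 140 / 4.14 = 33.82
- d: 160 / 4.9 = 32.65

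Line a reproduces. The other three ratios differ from it and from one another, so no single factor fits all four lines.

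**Printed mmol/L converted to mg/dL** (mmol/L × factor)

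| Line | Printed mmol/L | × 38.61 | × 38.67 | Printed mg/dL | Excess (mg/dL) |
|---|---|---|---|---|---|
| b | 3.37 | 130.1 | 130.3 | 120 | 10.1–10.3 |
| c | 4.14 | 159.8 | 160.1 | 140 | 19.8–20.1 |
| d | 4.9 | 189.2 | 189.5 | 160 | 29.2–29.5 |

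The 4.9 is printed to one decimal. If it is a rounded number rather than an exact cut-off, it covers 4.85 × 38.61 = 187.3 to 4.95 × 38.67 = 191.4 mg/dL, still at least 27 above 160.

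**Printed mg/dL converted to mmol/L** (mg/dL ÷ factor, at 38.61 and 38.67)

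- 120: 3.108 to 3.103
- 140: 3.626 to 3.620
- 160: 4.144 to 4.138

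The 4.14 printed beside 140 mg/dL in line c is therefore the conversion of the 160 mg/dL in line d.

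**Who falls between the two readings**

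- Category III: 120 to about 130 mg/dL
- Category II: 140 to about 160 mg/dL
- Category I: 160 to about 189 mg/dL

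Example: a Category I subject at 170 mg/dL passes 103 d in mg/dL, but 170 / 38.61 = 4.40 mmol/L, which is below 4.9.

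**Which figures fit the rest of the protocol**

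The mg/dL floors in lines d, c and b (160, 140, 120) are the Appendix D targets for Categories I, II and III, so a subject at or above the floor is not at goal, as the opening clause requires. The mmol/L figures would leave out subjects who are above goal. The Amendment 3 change list covers criteria 102, 104 and 105 but not 103, so this is current text.

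**The case against.** The strongest reply is that this is a misprint in a parenthesis with no shown consequence. The protocol leads with mg/dL throughout, several SAP lipid rules use mg/dL alone, and Appendix D is in mg/dL only, so a careful reader would know which figure was meant. Every wrong mmol/L value is stricter than its partner, so it could not have admitted anyone already at goal. Enrolment is over: SAP 10.1 refers to the completed primary analysis, which required all randomized subjects to have finished week 24 or left early. A formal amendment would need investigator agreement and IRB/IEC approval across about 40 sites.

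Much of this stands. The documents do point to mg/dL, the error runs in one direction, and the deviation example is hypothetical. A formal amendment would be out of proportion. It does not remove the point, however: the figures are wrong in a criterion that decides entry, no sentence gives mg/dL precedence, and the reporting unit is not stated. The one-decimal precision of 4.9 widens the equivalent for line d slightly but leaves a gap far beyond rounding.

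**Conclusion.** The concern holds: the mmol/L figures in 103 b, c and d are wrong as written. They are high by about 10, 20 and 29 mg/dL respectively, while line a is correct. The result rests only on the protocol's own conversion pairs, and no factor consistent with those pairs changes it. That the error lies in the mmol/L figures, not the mg/dL ones, is inferred from Appendix D and the opening clause of 103.

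Whether any subject was affected cannot be settled from the documents, since they do not give the unit in which screening LDL-C was reported or applied. If only mg/dL was used, nobody was affected. If mmol/L was used anywhere, the effect was exclusion before randomization. The sample size and power figures do not depend on this point. What remains at stake is the accuracy of the eligibility text and of the deviation listing. It should be fixed.

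**What to change.** Reconcile the two units so that each line of 103 states one threshold. The mg/dL values that match Appendix D convert to 3.10, 3.62 and 4.14 mmol/L at 38.67, or 3.11, 3.63 and 4.14 at the protocol's 100/2.59. Use one factor throughout, and add a sentence that mg/dL governs. With enrolment closed, an erratum or note to file is enough.

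Send one query to confirm the unit used for the eligibility decision by the central laboratory, the sites and the IVRS/IWRS. If the answer is mg/dL only, record that and close the point. If mmol/L was used anywhere, review the screen failures and eligibility deviations in the three bands given above and report the counts in the clinical study report.

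The cost is three numbers, one sentence and one query. A review of screening records is needed only in the second case, and no analysis has to be rerun for the correction itself.

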4.1.2 Exclusion Criteria

201 History of hemorrhagic stroke

202 Personal or family history of hereditary muscular disorders

203 NYHA III or IV heart failure, or last known left ventricular ejection fraction (LVEF) $< 30\%$

204 Uncontrolled serious cardiac arrhythmia defined as recurrent and highly symptomatic ventricular tachycardia, atrial fibrillation with rapid ventricular response, or supraventricular tachycardia that are not controlled by medications, in the past 3 months prior to randomization

205 Myocardial infarction, unstable angina, percutaneous coronary intervention (PCI), coronary artery bypass graft (CABG) or stroke within 3 months prior to randomization

206 Planned cardiac surgery or revascularization

207 Type 1 diabetes, poorly controlled type 2 diabetes (HbA1c $> 9.0\%$), newly diagnosed type 2 diabetes (within 6 months of randomization), or laboratory evidence of diabetes during screening (fasting serum glucose ≥ 126 mg/dL [7.0 mmol/L] or HbA1c $\geq 6.5\%$) without prior diagnosis of diabetes

208 Uncontrolled hypertension defined as sitting systolic blood pressure (SBP) > 160 mmHg or diastolic BP (DBP) > 100 mmHg

209 Subject has taken in the last 4 weeks prior to LDL-C screening red yeast rice, > 200 mg/day niacin, or prescription lipid-regulating drugs (eg, fibrates and derivatives) other than **low (lowest available recommended starting dose approved by the Japanese Ministry of Health, Labour and Welfare) or atypical dose of statins, ezetimibe, bile-acid sequestering resin, or stanols and stanol esters**

-
- 210 Subject who has taken a cholesterylester transfer protein (CETP) inhibitor in the last 12 months prior to LDL-C screening, such as: anacetrapib, dalcetrapib or evacetrapib
- 211 Treatment in the last 3 months prior to LDL-C screening with any of the following drugs: systemic cyclosporine, systemic steroids (eg, IV, intramuscular [IM], or PO) (Note: hormone replacement therapy is permitted), vitamin A derivatives and retinol derivatives for the treatment of dermatologic conditions (eg, Accutane); (Note: vitamin A in a multivitamin preparation is permitted)
- 212 Uncontrolled hypothyroidism or hyperthyroidism as defined by thyroid stimulating hormone (TSH) < 1.0 time the lower limit of normal or > 1.5 times the ULN, respectively, at screening. Potential subjects with TSH < 1.0 time the lower limit of normal due to thyroid replacement therapy is not considered an exclusion
- 213 Moderate to severe renal dysfunction, defined as an estimated glomerular filtration rate (eGFR) < 30 ml/min/1.73m² at screening
- 214 Active liver disease or hepatic dysfunction, defined as aspartate aminotransferase (AST) or alanine aminotransferase (ALT) > 3 times the ULN as determined by central laboratory analysis at screening
- 215 CK > 3 times the ULN at screening
- 216 Known active infection or major hematologic, renal, metabolic, gastrointestinal or endocrine dysfunction in the judgment of the investigator
- 217 Diagnosis of deep vein thrombosis or pulmonary embolism within 3 months prior to randomization
- 218 Unreliability as a study participant based on the investigator's (or designee's) knowledge of the subject (eg, alcohol or other drug abuse, inability or unwillingness to adhere to the protocol, or psychosis)
- 219 Female subject who has either (1) not used (an) acceptable method(s) of effective birth control (see below) for at least 1 month prior to screening and (2) is not willing to inform her partner of her participation in this clinical study and to use such (an) acceptable method(s) of effective birth control during treatment with SC IP (evolocumab/placebo) and for an additional 15 weeks after the end of treatment with SC IP (evolocumab/placebo), unless the female subject is sterilized or postmenopausal (see below);
- a. A female is considered of childbearing potential unless sterilized or postmenopausal with menopause defined as:
- i. 12 months of spontaneous and continuous amenorrhea in a female ≥ 55 years old, or
 - ii. 12 months of spontaneous and continuous amenorrhea with a follicle-stimulating hormone (FSH) level > 40 IU/L (or according to the definition of "postmenopausal range" for the laboratory involved) in a female < 55 years old, or
 - iii. The subject has undergone bilateral oophorectomy

- b. Acceptable methods of preventing pregnancy include not having intercourse (sexual abstinence), surgical contraceptive methods – (vasectomy of the male partner **[and testing shows there is no sperm in the semen]** or bilateral tubal ligation/occlusion), or use of hormonal birth control methods (pills, patches), intrauterine devices (IUDs), **intrauterine hormonal-releasing system (IUS), male partner uses a condom with or without spermicide, use of a cervical cap, diaphragm, or contraceptive sponge with spermicide**; or two (2) barrier methods (each partner must use one barrier method) with spermicide – males must use condom with spermicide; females must choose either diaphragm with spermicide, OR cervical cap with spermicide, OR contraceptive sponge with spermicide.
- c. Note: If additional medications are given during treatment which may alter the contraceptive requirements (these additional medications may require an increase in the number of contraceptive methods and/or length of time that contraception is to be utilized **and/or length of time breastfeeding is to be avoided** after the last dose of protocol-required therapies) the investigator is to discuss changes with the study subject.

- 220 Subject who is pregnant or breast feeding, or planning to become pregnant or breastfeed during treatment with SC IP (evolocumab/placebo) and/or within 15 weeks after the end of treatment with SC IP (evolocumab/placebo)
- 221 Subject who has previously received evolocumab or any other therapy to inhibit PCSK9
- 222 Subject who has any kind of disorder that, in the opinion of the investigator, may compromise the ability of the subject to give written informed consent and/or to comply with all required study procedures
- 223 Malignancy except non-melanoma skin cancers, cervical or breast ductal carcinoma in situ within the last 5 years
- 224 Subject who has known sensitivity **or intolerance** (eg, allergy or serious adverse reaction to ezetimibe) to any of the products or components to be administered during dosing
- 225 Subject who is likely to not be available to complete all protocol-required study visits or procedures, and/or to comply with all required study procedures (eg, Patient Reported Outcomes [PROs]) to the best of the subject and investigator's knowledge
- 226 History or evidence of any other clinically significant disorder, condition or disease (with the exception of those outlined above) that, in the opinion of the investigator or Amgen physician, if consulted, would pose a risk to subject safety or interfere with the study evaluation, procedures or completion
- 227 Currently enrolled in another investigational device or drug study, or less than 30 days since ending investigational device or drug study(ies), or receiving other investigational agent(s) or procedures

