Evolocumab will be administered using a spring-based prefilled autoinjector/pen (prefilled AI/Pen) or 3.5 mL Personal Injector.

Evolocumab will be administered at 1 of 2 regimens:

Evolocumab 140 mg SC Q2W (1 prefilled AI/Pen injection) or

Evolocumab 420 mg SC QM (3 prefilled AI/Pen injections or 1 Personal Injector injection)

Non Amgen Investigational Product Dosage and Administration: Ezetimibe 10 mg (and placebo) will be provided by Amgen (or designee) and will be taken by the subject PO QD. Placebo will be matching ezetimibe by over-encapsulation.

Amgen will not provide Standard of Care (SOC) medication for the open label period.

Summary of Subject Eligibility Criteria: Males and females, ≥ 20 to ≤ 80 years of age, **Japanese by self-identification**, are eligible for this study. Subject must have tried and failed at least 2 statins with failure to at least 1 of the statins at an average daily dose at or below the following doses due to intolerable myopathy, ie, myalgia (muscle pain, ache, or weakness without CK elevation), myositis (muscle symptoms with increased CK levels), or rhabdomyolysis (muscle symptoms with marked CK elevation). For subjects that developed rhabdomyolysis, defined as CK $> 10 \times$ ULN, failure of only 1 statin at any dose is acceptable.

- Atorvastatin 10 mg
- Fluvastatin 20 mg
- Pravastatin 10 mg
- Rosuvastatin 2.5 mg
- Simvastatin 5 mg
- Pitavastatin 1 mg
- For unlisted statins, the average daily dose should not exceed the lowest available recommended starting dose approved by the Japanese Ministry of Health, Labour and Welfare.

Symptoms must have resolved **or improved** when statin was discontinued or the dose was reduced. Depending on a subject's management category per 2012 JAS guideline (see [Appendix D](#)) subjects must meet criteria provided. Fasting triglycerides must be ≤ 400 mg/dL (4.5 mmol/L) as determined by the central laboratory analysis at screening.

Major exclusion criteria include, but are not limited to moderate to severe heart failure, uncontrolled cardiac arrhythmia, symptomatic coronary artery disease within the last 3 months, recently diagnosed or poorly controlled diabetes, hypertension or hyper/hypothyroidism, known active infection or major hematologic, renal, hepatic, metabolic, gastrointestinal or endocrine dysfunction, systemic steroid use, pregnancy or lactation, previous exposure to evolocumab or other PCSK9 inhibitor.

Statistical Considerations:

General Considerations

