2.3 Non-Amgen Medicinal Product Background

Ezetimibe 10mg tablets will be provided during study participation. Ezetimibe will be over-encapsulated to maintain blinding.

Ezetimibe is in a class of lipid-lowering compounds that selectively inhibits the intestinal absorption of cholesterol and related phytosterols. Ezetimibe is approved in Japan for treatment of hypercholesterolemia, familial hypercholesterolemia, and homozygous

sitosterolemia. For patients with homozygous familial hypercholesterolemia, ezetimibe should be used as an adjunct to HMG-CoA reductase inhibitor and other lipid-lowering non-pharmacological treatments (eg, LDL apheresis) or when such treatments are unavailable.

In the double blind placebo-controlled study of 100 Japanese hypercholesterolemia patients described in the label with a treatment duration of 12 weeks, LDL-C, total cholesterol, TG were reduced by 18.1%, 12.8% and 2.2%, respectively. HDL-C was increased by 5.9%.

In the ezetimibe clinical studies of 504 Japanese patients described in the label, 18.8% of patients on ezetimibe reported adverse reactions. The most commonly reported adverse reactions were constipation (3.0%), erythema (2.4%), diarrhea (2.2%), abdominal pain (2.0%), abdominal distension (1.6%), and nausea and vomiting (1.6%).

Ezetimibe is contraindicated in the following circumstances: in combination with a statin in patients with severe liver dysfunction and in patients with a known hypersensitivity to ezetimibe.

The recommended dose of ezetimibe is 10 mg once daily, administered after meal.

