6.2.2.1.2 Dosage Adjustments, Delays, Rules for Withholding or Restarting, Permanent Discontinuation

No dosage adjustment is necessary in patients with mild hepatic or renal impairment. No dosage adjustment is necessary in geriatric patients. Additional details regarding ezetimibe are provided in the IPIM.

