6.7 Excluded Treatments and/or Procedures During Study Period

The following treatments are not permitted during the study:

- Prescription lipid regulating medications (eg, non-study ezetimibe, or fibrates and derivatives)
- **However, the following agents are allowed:**
 - bile-acid sequestering resin
 - stanol and stanol esters
 - **Please note: subjects on a low (lowest available recommended starting dose approved by the Japanese Ministry of Health, Labour and Welfare) or atypical dose of statins may continue their current dose if the subject has taken it for at least 4 weeks prior to the screening; new statin initiations, and/or dose adjustments are not permitted during screening or the study itself.**
- Red yeast rice, niacin > 200 mg per day
- Any other drug that significantly affects lipid metabolism (eg, systemic cyclosporine, systemic steroids [IV, IM, or PO] (*Note: hormone replacement therapy is permitted, vitamin A derivatives and retinol derivatives for the treatment of dermatologic conditions [eg, Accutane]*). Vitamin A as part of a multivitamin preparation is permitted.

- Prescribed amphetamines, or amphetamine derivatives, and weight loss medications.

Should there be a clinical need to prescribe one of these treatments, the investigator should call the Amgen Medical Monitor to discuss.

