10.1.3 Covariates and Subgroups

Baseline covariates include, but are not limited to:

- Stratification factors:
 - Screening LDL-C level: < 180 mg/dL [4.7 mmol/L] vs. ≥ 180 mg/dL
 - Baseline statin use: yes vs. no

The following baseline covariates may be used for subgroup or covariate analyses with the subgroups as specified or in their original format:

- Age: < 65 years, ≥ 65 years; < 75 years, ≥ 75 years
- Sex
- LDL-C: < baseline median, ≥ baseline median
- PCSK9 level: < baseline median, ≥ baseline median
- Baseline lipid regulating medications use: yes vs. no

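### No eligibility criterion carries over the stated contraindication to ezetimibe with a statin in severe liver dysfunction, and the synopsis and criteria 214, 216 and 226 do not agree on the liver

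*Protocol*

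**What the plan says.** The contraindication is in protocol section 2.3: "Ezetimibe is contraindicated in the following circumstances: in combination with a statin in patients with severe liver dysfunction". The same sentence gives a second one, known hypersensitivity to ezetimibe.

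Statin users are admitted. Under criterion 105, subjects on a low or "atypical dose of statin must be on a stable dose for at least 4 weeks prior to screening", and section 6.7 says that they "may continue their current dose if the subject has taken it for at least 4 weeks prior to the screening". Section 10.1.3 lists "Baseline statin use: yes vs. no" as a stratification factor, so such subjects are expected.

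The liver appears in the eligibility text as follows:

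- **Synopsis, eligibility summary:** the exclusions include "known active infection or major hematologic, renal, hepatic, metabolic, gastrointestinal or endocrine dysfunction".
- **Criterion 214:** "Active liver disease or hepatic dysfunction, defined as aspartate aminotransferase (AST) or alanine aminotransferase (ALT) > 3 times the ULN", measured by the central laboratory at screening.
- **Criterion 216:** "Known active infection or major hematologic, renal, metabolic, gastrointestinal or endocrine dysfunction in the judgment of the investigator".
- **Criterion 226:** a catch-all for other clinically significant conditions that the investigator or a sponsor physician considers a risk. It exempts conditions already set out in the list.

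On ezetimibe dosing, section 6.2.2.1.2 says "No dosage adjustment is necessary in patients with mild hepatic or renal impairment". It is silent on worse hepatic impairment and refers to the product manual (IPIM) for further detail.

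**The concern.** The protocol names a combination and a patient group in which the comparator should not be used, admits users of one half of that combination, and then randomises them to the other half. One would expect an eligibility criterion to mirror the contraindication. The criterion for sensitivity or intolerance to study products (224) mirrors the hypersensitivity part. Nothing mirrors the liver part.

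The liver exclusion that does exist rests on transaminases alone. The judgement-based list that could have backed it up lacks the one organ that the synopsis version of the list includes. What is at stake is the safety of a small, specific group of subjects, and whether sites screen against the same rule that the synopsis describes.

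**Working it through.** The question is whether a subject inside the stated contraindication can pass the criteria as written. Take a subject who takes a stable low statin dose, has severe liver dysfunction, and has AST and ALT both at or below 3 times ULN at screening.

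| Text | What it tests | Does it exclude this subject? |
|---|---|---|
| 105, 209, section 6.7 | Statin dose low or atypical, and stable | No, admits |
| 214 | AST or ALT above 3 times ULN | No, both are at or below the limit |
| 216 | Investigator's judgement on named organ systems; liver not named | Not by its terms |
| 224 | Sensitivity or intolerance to study products | No |
| 226 | Opinion on other conditions, exempting those already listed | Uncertain |

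No eligibility limit in section 4.1 uses bilirubin, albumin, INR or a history of liver disease, although bilirubin and albumin are in the screening chemistry panel.

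**Does criterion 214 explain the missing word in 216?** Compare the other organ systems. Renal function has a numeric criterion (213), and 216 still lists renal. Diabetes and thyroid disease have criteria 207 and 212, and 216 still lists metabolic and endocrine. In each case the judgement criterion stands behind the numeric one. The liver is the exception.

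**Does criterion 226 close the gap?** There are two readings. Severe dysfunction below the transaminase limit may be a condition not yet listed, so that 226 applies. Or hepatic dysfunction is already listed in 214 with its own threshold, so that 226 exempts it. The text does not settle which is meant.

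**Chance of ezetimibe.** The allocation in section 3.1 is 2:2:1:1, with the last two groups on ezetimibe:

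(1 + 1) / (2 + 2 + 1 + 1) = 2/6 = 1/3.

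The documents give no number of such subjects. As an illustration only, assume k of them, assigned independently. The chance that at least one receives ezetimibe is 1 − (2/3)^k:

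- k = 1: 33%
- k = 2: 1 − 4/9 = 56%
- k = 3: 1 − 8/27 = 70%

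**Effect on the sample size.** The plan's own figure reproduces. Section 10.2 has 40 and 20 subjects less 5%, so 38 and 19, with difference 20, SD 20 and two-sided alpha 0.05. The noncentral t calculation gives 93.8%, against the stated figure of at least 93%. None of these inputs depends on the liver criteria.

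**The case against.** The strongest reply is that the full list does contain a hepatic exclusion. Criterion 214 is two items above 216, the synopsis is a summary that may simply be paraphrasing 214, and section 4 sends sites to section 4.1 for the full criteria. This stands as far as it goes. A reader might infer from 216 alone that liver disease is not excluded at all, and 214 shows that this is wrong. It does not remove the gap, because 214 sees only transaminases.

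A second reply is that investigators have medical history, physical examination and chemistry at screening, and can use 226. That is true, and a careful investigator may well exclude the subject. But exclusion then depends on opinion and on how the exemption in 226 is read.

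Third, the IPIM may carry the contraindication. It is not available here, so this cannot be ruled out. It would still leave the protocol's own texts in disagreement.

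Several stronger readings are tempting and not supported:

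- **That the missing word is the cause, and restoring it the cure.** Criterion 216 is itself a matter of judgement, so one more word could not guarantee that no contraindicated subject is randomised. The transaminase-only definition in 214 and the lack of any criterion mirroring section 2.3 matter more.
- **That the protocol plans to enrol such subjects.** HCV viral load follow-up does not imply severe liver dysfunction, and the known active infection clause of 216 may exclude some of these subjects. Section 6.3.2 mentions underlying liver disease, but it also refers to eligibility criteria on normal transaminases and bilirubin that do not exist here, so it looks like unadapted template text.
- **That blinding creates the risk.** The eligibility decision precedes randomisation, when the investigator knows that any subject may receive ezetimibe. Section 5.2 allows unblinding when it is essential for management.
- **That the safety comparison is distorted.** One event is 1/20 = 5 points in the ezetimibe group and 1/40 = 2.5 points in the evolocumab group, but that holds for any event in this trial. The SAP plans no inference on adverse events or safety laboratory data.

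**Conclusion.** The point holds as a narrow gap between texts that bears on safety. A statin user with severe liver dysfunction who is under the limit in 214 meets the objective criteria, and the only backstop is ambiguous. The size is a 1 in 3 chance of ezetimibe for each such subject; how many there would be is unknown, and probably few.

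The conclusion assumes that severe liver dysfunction can occur with AST and ALT at or below 3 times ULN, that section 2.3 is meant to bind in this trial, and that no document outside the protocol and SAP closes the gap. It does not claim that such a subject would be enrolled in practice. It has no bearing on the estimated treatment effect.

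**What to change.** The sponsor should reconcile the synopsis, criteria 214, 216 and 226, section 2.3 and section 6.2.2.1.2. After that:

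- the list used at screening should agree with the synopsis on the liver and with the contraindication the protocol states;
- the exemption in 226 should make clear whether it covers liver disease that falls short of the threshold in 214;
- section 6.2.2.1.2 should match the range of hepatic function that the criteria admit.

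Which liver definition or limit is right is a clinical decision for the sponsor, and none is proposed here. The cost is a wording change in an amendment and at most a few extra screen failures. No change to the sample size, randomisation or analysis is needed.
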